### **9.1.3 Statistical analysis procedures**

Relevant links involved in the statistical analysis will be in accordance with the requirements in ICH E9 and the relevant requirements in the "*Guidelines for Biostatistics of Clinical Trials*" issued by the National Medical Products Administration (NMPA). Meanwhile, all statistical analysis processes will be performed in strict accordance with the Standard Operating Procedures (SOP) formulated by the Medical Statistics Department of the National Center for Cardiovascular Diseases.

## **9.2 Calculation of sample size**

### **9.2.1 Total sample size**

The total number of patients enrolled in this study is planned to be 106. The sample size is determined based on a combination of study hypothesis and estimates of expected levels of efficacy, and is calculated on a statistical basis. The sample size is calculated based on the primary endpoint index, *i.e.*, the success rate of Qubic Stim cardiac stimulator to send diagnostic electrical stimulation to the heart. Due to the limited reference materials for similar products, the "*Guidelines for the Technical Review of the Registration of Implantable Cardiac Electrode Lead Products*" combined with the opinions and recommendations of cardiac electrophysiological clinical experts, the target value of the primary index is set at 90%. Meanwhile, assuming that the expected success rate of the investigational product can reach 98%, when the significance level of the statistical test is 0.025 on one side, and the assurance level is 90%, considering the largest possible drop-out rate in the study

is 5%, and using the accurate probability method in combination, the sample size is finally set at 106 cases. The corresponding sample size calculation formula is:

$$n = \frac{[\mu_{1-\alpha}\sqrt{p_0(1-p_0)} + \mu_{1-\beta}\sqrt{p_T(1-p_T)}]^2}{(p_T - p_0)^2}$$

Here,  $p_T$  represents the predicted success rate level of the test product and  $p_0$  represents the corresponding target value;  $\mu$  represents the quantile corresponding to the standard normal distribution,  $\alpha$  corresponds to the type I error level of the statistical test, and it is 0.025 here, while  $\beta$  corresponds to the type II error level of the statistical test, and it is 0.1 when calculation (corresponding to 90% power level).

According to the clinical practice, the estimated screening failure rate is expected to be 20%, so the estimated total number of screening cases is 133.

### **9.2.2 Case number of each disease in the clinical trial and the determination reasons**

This trial protocol strictly limits the selected patients according to the inclusion/exclusion criteria. It can be considered that the current study is only conducted in patients with a single indication. The above 106 patients belong to the same disease group and will not be further divided.

### **9.2.3 The minimum and maximum subject numbers of each clinical trial institution in the multi-center clinical trial and the reasons**

This trial will be conducted in multiple clinical trial institutions at the same time. In principle, the number of participants in centers will be distributed as evenly as possible to ensure sufficient center representativeness. However, considering the feasibility and actual progress of enrollment, the number of enrollment will be adjusted in accordance with the actual situation to ensure that the number of each center's participants is relatively balanced, and for a particular center, its final size should not exceed 50% of the total.

## **9.3 Significance level and power of the clinical trial**

In this trial, the significance level and the power of the statistical test are 0.05 on both sides (except for otherwise stated) and the assurance degree of test is 90%, respectively.

## **9.4 Predicted drop-out rate**

In the sample size design process, the largest possible drop-out rate in the study period is expected to be 5%. The drop-out includes all cases that ultimately cannot be included in the main analysis, and usually refers to significant violations of the study protocol judged by the principal

investigator. The possible situations include (not limited to): patients do not meet the inclusion/exclusion criteria; patients do not use any study-related products; patients use third-party products other than the study; patients do not complete follow-up as required; follow-up time windows exceed the set time limit; there are concomitant treatments that affect efficacy. All of the above will be included in the total drop-out rate.

## **9.5 Qualified/unqualified criteria of the clinical trial results**

From a statistical perspective, judging whether the clinical trial results are qualified or not is equivalent to verifying the initial hypothesis. In this study, the primary evaluation index is the success rate of Qubic Stim cardiac stimulator to send diagnostic electrical stimulation to the heart. By comparing the trial results with pre-set target values, it is confirmed that the test product meets the clinical application requirements.

In summary, the determination of the trial results will be based on the comparison between the test product stimulation success rate and target value. If the results show that the lower limit of the 95% confidence interval of the test product success rate exceeds 90% (a preset target value), a positive result can be considered to indicate that the test product can meet the requirements of clinical application.

## **9.6 Criteria and reasons for terminating the trial for statistical reasons**

This trial does not pre-set mid-term analysis and corresponding early termination criteria, so it is inapplicable here. All statistical analysis is performed after the data are collected, cleaned and finally locked.

## **9.7 Statistical methods for all data, including missing, unused and erroneous data (including halfway withdrawal by the subjects or the investigators) and treatment of unreasonable data**

The statistical analysis process (procedure) is implemented in strict accordance with the Standard Operating Procedures (SOP) of the Medical Statistics Department of the National Center for Cardiovascular Diseases. Please refer to related documents for details.

For the missing data that may appear in the study process, the analysis will deal with the missing main efficacy indicators. The specific treatment methods will be explained in the statistical analysis plan. At the same time, we will also use Tipping Point critical point method for sensitivity analysis of the impact of missing data. For other missing indexes, we will analyze the data that are actually observed directly rather than by cut-off processing.

Erroneous and unreasonable data will be processed in the data cleaning process before statistical analysis. Information on patients who withdraw from the trial by themselves or by the investigators will still be included into the final statistical analysis. The statistical report will detail all the withdrawals by the patients or the investigators, and missing primary indexes resulting from early withdrawals will be treated according to the above treatment strategy for missing data.

## **9.8 Procedures for reporting deviation of original statistical plan**

The statistical analysis proposal needs to be confirmed by the sponsor and the principal investigator, and finalized before the data are locked. Prior to finalization, the initial analysis plan can be modified in accordance with the actual situation during the trial. In principle, the main analysis principles, methods and analysis sets will not be modified, and all modifications will be recorded.

## **9.9 Criteria for selection of subjects incorporated into the analysis and its reasons**

The statistical analysis will be performed on the basis of the following analysis populations, which will be clearly defined before the start of the statistical analysis. The analysis populations in this study include:

**Full Analysis Set (FAS):** An analysis set that is determined in accordance with the Intention To Treat principle, which will include all subjects who participates in the trial (recorded in the central registry) and do use the investigational product.

**Per Protocol Set (PPS):** refers to all subgroups of patients who have completed the trial without significant protocol deviation (referring to the study subject's violation of the inclusion/exclusion criteria, *etc.*).

**The analysis of the primary efficacy indexes will be performed on the basis of the FAS and the PPS; all baseline demographic data and secondary efficacy analysis will be performed on the basis of the FAS, and the safety evaluation will also be based on the FAS. (So SS is not defined separately).**

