#### **8.1.7.2 Method and time selection for valuation, record and analysis of safety parameters**

All adverse events shall be recorded throughout the study. However, only the serious adverse events that are definitely, likely or possibly related to Qubic Stim cardiac stimulator will become the basis of SADE event rate.

SADE related to Qubic Stim cardiac stimulator is defined but not limited to: serious adverse device events caused by failure to start-up, current failure to output, leakage current and other reasons. These will be recorded as SADE related to Qubic Stim cardiac stimulator. But in cases where electrical stimulation is known to cause potentially life-threatening arrhythmias, many times inducing these arrhythmias is the purpose of an electrophysiological examination. Therefore, any tachycardia events caused by programmed electrical stimulation in this study will not be included in SADE.

The important parameter  $P_{SADE}$  is the rate of serious adverse events that may be related to Qubic Stim cardiac stimulator for each subject, which is equal to the number of SADE divided by the number of subjects.

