#### 9.1.2 Statistical analysis methods

1) Descriptive analysis: Counting data is described by frequency and constituent ratio; while measurement data is described by mean, standard deviation, median, the 25th and 75th quantiles, maximum, and minimum.

2) Baseline demographic analysis: Descriptive analysis will be the main method. For subgroups comparison that may be involved, the likelihood data  $\chi^2$  test will be used between counting data groups. When the theoretical frequency of more than 25% of the cells is less than 5, the Fisher exact probability method will be used. Grouped t-test is used for comparisons between groups with normally distributed measurement data; while Wilcoxon Rank Sum test used for comparisons between groups with non-normally distributed measurement data.

3) Efficacy analysis: All patients who use the investigational product will be included in the analysis. For the primary efficacy indexes, the asymptotic normal method and accurate probability method will be used to estimate the stimulation success rate and its 95% confidence interval, and the lower limit of the confidence interval are compared with the set target values to determine whether the test product meets the needs of clinical application. Meanwhile, the Tipping Point method will also be used to perform a sensitivity analysis on the potential impact of missing data. For the filled data, the asymptotic normal method and accurate probability method are also used to estimate the product success rate and 95% confidence interval, respectively. The statistical analysis method to be used for other efficacy indexes is the same as the baseline; for intra-group

comparisons that may be involved in specific indexes, paired t test is used for comparisons between groups with normally distributed measurement data; while Wilcoxon Rank Sum test used for comparisons between groups with non-normally distributed measurement data; and for intra-group comparison of qualitative indexes, the McNemar paired  $\chi^2$  test is used.

4) Safety evaluation: Adverse events are described by the number and incidence of adverse events; meanwhile, the specific manifestation, severity and relationship between all the adverse events are described in detail.

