## **11.2 Analysis of failure possibility**

The possibility of test failure involves: 1. The subjects fail to complete electrical cardiac stimulation test safely. 2. The cardiac stimulator cannot conduct pace-making and pace the heart or fail to measure the electrical conduction time. 3. The investigators fail to operate and collect data in accordance with the test requirements. In order to avoid test failure, the investigators shall be fully trained, the subjects shall be fully informed, and the study shall be conducted in strict accordance with the trial protocol.

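### The primary analysis set depends on an undefined word, *use*, so a subject whose stimulator will not start can be dropped instead of counted as a failure

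*Combined protocol and SAP*

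**What the plan says.** Section 9.9 describes the FAS as following the intention-to-treat principle, then restricts it to a set "which will include all subjects who participates in the trial (recorded in the central registry) and do use the investigational product". Section 9.1.2 sets the same condition for efficacy: "All patients who use the investigational product will be included in the analysis". Neither says whether use means an attempt, connection, power-on or a delivered stimulus.

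The set carries both main results. For the primary endpoint, "The analysis of the primary efficacy indexes will be performed on the basis of the FAS and the PPS". For safety, "the safety evaluation will also be based on the FAS. (So SS is not defined separately".

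Section 9.4 adds: "The drop-out includes all cases that ultimately cannot be included in the main analysis". Its examples include "patients do not use any study-related products" and, next in the list, subjects in whom a third party's product is used.

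The protocol expects that the device may fail at the start. Section 8.1.7.2 counts as device-related "serious adverse device events caused by failure to start-up, current failure to output, leakage current and other reasons". Section 11.2 lists, among the ways the test may fail, "The cardiac stimulator cannot conduct pace-making and pace the heart".

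Success (sections 1 and 8.1.6.2) requires all three functions to reach the standard in the subject: programmed extrastimulation, burst and sinus node recovery time. Section 9.5 calls the trial positive if the lower limit of the 95% interval exceeds 90%.

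**The concern.** In a single-arm trial of device success against a fixed target, a device that will not start is the plainest failure there is. The success definition makes such a subject a failure only once the subject is in the analysis set. Entry to that set depends on use, and no sentence says that a failed attempt is use. If the examination is then done with another stimulator, the subject fits both drop-out examples in section 9.4.

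Removing a failure lowers the denominator and leaves the number of successes unchanged, so the estimate and its lower limit can only rise. A false claim that the target is met becomes more likely. Because safety uses the same set, a serious event tied to a start-up failure could also leave the device-event rate. If the meaning of use is settled only when such a case occurs, it is settled with the outcome known.

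**Working it through.** **Inputs.** From section 9.2.1: target 90%, expected success 98%, one-sided significance level 0.025, power 90%, drop-out 5%, exact method used in combination, 106 subjects. From section 9.5: lower 95% limit above 90%. The documents give no rate of start-up failure, so every such rate below is an assumption.

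**The plan's own sample size.** The printed formula gives n = [1.960·√(0.90·0.10) + 1.2816·√(0.98·0.02)]² / 0.08² = 92.02, so 93. Under the exact (Clopper-Pearson) rule, the smallest n from 93 upward with at least 90% power is 100 (at least 96 successes, power 94.9%). Then 100/0.95 = 105.3, so 106. The stated figure is reproduced.

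**How many failures the rule allows.** For x successes in n, the exact lower limit is the 2.5% quantile of Beta(x, n − x + 1).

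- 102/106: 0.906, pass.
- 101/106: 0.893, fail.

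So 4 failures are allowed at n = 106. The allowance is still 4 at every n from 100 to 106. Dropping up to six no-starts therefore uses up none of it.

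**Examples with 106 enrolled.**

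| Assumed outcome | All counted | No-starts excluded |
|---|---|---|
| 1 no-start, 4 other failures | 101/106, 0.893, fail | 101/105, 0.905, pass |
| 5 no-starts, no other failure | 101/106, 0.893, fail | 101/101, 0.964, pass |
| 6 no-starts, 2 other failures | 98/106, 0.857, fail | 98/100, 0.930, pass |

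One exclusion is enough to reverse the result.

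**Chance of a positive trial when true success over all subjects is 90%.** Let q be the share of all subjects who are excluded no-starts. The number excluded, K, is binomial(106, q). Success among those left is 0.90/(1 − q); for q = 1% this is 0.90/0.99 = 0.909. The chance is the sum over k of P(K = k) times the probability of reaching the exact critical count at n = 106 − k.

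| q (assumed) | Expected number, 106·q | Chance of a positive trial |
|---|---|---|
| 0 | 0 | 1.6% |
| 0.5% | 0.53 | 2.3% |
| 1% | 1.06 | 3.3% |
| 2% | 2.12 | 6.7% |
| 3% | 3.18 | 12.5% |

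The planned 2.5% still holds at 0.5% and is exceeded at 1%.

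**Power with all 106 counted.** If the 98% already includes no-starts, the probability of at least 102 successes in 106 is 93.8%. If the 98% describes only subjects whose device starts, overall success is 0.98·0.99 = 0.9702 with 1% no-starts and 0.98·0.98 = 0.9604 with 2%, and power is 79.0% and 59.0%.

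**The case against.** The best counter-argument comes from the safety endpoint. Section 8.1.7.2 counts serious events caused by failure to start or to deliver output, and section 9.9 bases safety on the FAS. If a failed start were not use, the event rate could not contain events that it names. That favours reading use as attempted use, and such a subject then stays in and fails. The inference is fair, but it is only an inference: no sentence states it, and the drop-out wording in section 9.4 points the other way.

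Section 9.4 is a drop-out forecast, not a definition of an analysis set. It says that drop-out usually means a significant protocol violation, and a malfunction is not one. But it defines drop-out as absence from the main analysis, and its list covers non-use and third-party products without regard to cause.

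Section 9.7 keeps withdrawn subjects and adds a tipping-point analysis. A start-up failure is not a withdrawal, though. Even for withdrawals the primary value is handled as missing, by a method left to the analysis plan, and not as failure. Section 9.9 promises clear definitions before analysis, which is the place to settle the matter.

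Two further points stand. Section 11.2 mostly describes a device failing while in use, and those subjects are in the FAS. A device that powers on but gives no output has arguably been used, so the concern is weaker there.

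**Conclusion.** The point holds as a gap in the definition of the analysis set. Use is undefined, section 9.4 permits a no-start to be treated as drop-out, and no rule scores that subject as a failure. The clearest case is a device that will not start, followed by a switch to another stimulator.

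A reader might infer that the plan expressly excludes device failures, or analyses only subjects in whom the device works. The documents do not say that. The condition is on use, and a device that paces but fails burst or recovery-time measurement stays in as a failure.

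A reader might also assume a very large error rate. The chance of a false positive reaches 34% only if 5% of all subjects, about 5 of 106, are start or output failures and every one is excluded. Nothing in the documents supports such a rate. At assumed rates of 0.5% to 3% the chance runs from 2.3% to 12.5%, against 1.6% with all counted. All these figures assume a true success rate of 90%, the exact rule, and exclusion of every no-start.

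**What to change.** - **Sections 9.9 and 9.1.2:** define the FAS as all enrolled subjects in whom use of the Qubic Stim was attempted, meaning connected or switched on for the examination. Add no eligibility condition; the present FAS has none, and one would narrow it.
- **Primary endpoint:** score failure to start, failure to deliver output, and a switch to another stimulator because of device failure as failures.
- **Section 9.4:** limit the non-use and third-party-product categories to reasons unrelated to the device.
- **Section 9.7:** state that the device-caused cases are failures and not missing data.

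The safety set follows the FAS, so the device-event rate is repaired by the same change.

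The cost is a few sentences and one case report form item recording attempted use. The sample size stays at 106, with exact power of 93.8% if the 98% covers every subject in whom use is attempted; the sponsor should confirm that it does. The downside is that the observed success rate may be slightly lower.

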# **10 Data Management**

## **10.1 CRF**

Original data shall be collected from each study site, recorded in CRF and then verified by CRF.

## **10.2 Device data in CRF**

All preset parameters of ECG stimulator shall be recorded in CRF, which can be downloaded or printed by multi-channel analyzer and saved as original data.

## **10.3 Data quality control**

Biotronik shall verify the study data. At any time, Biotronik or the investigators approved by each study site shall report the completed and missing data. After CRF data is input into the database, the validity, consistency, deficiency and normal range of data shall be checked by the logic examination program. The data manager shall timely solve any problem discovered, those problems can be solved by making a judgment through comparing the data with that in other parts of CRF, as well as issuing data query table to the investigator.

# **11 Feasibility Analysis**

## **11.1 Possibility analysis of success**

The safety and performance of Qubic Stim electrical cardiac stimulator has been analyzed through the clinical evaluation report mentioned above, and it can be inferred that the trial results can be extended to ordinary Chinese patients.

Considering that the follow-up period is short and the subjects show good compliance, there will not be a large number of subjects lost to follow-up. Therefore, sufficient clinical data can be obtained during the trial.

## **11.2 Analysis of failure possibility**

The possibility of test failure involves: 1. The subjects fail to complete electrical cardiac stimulation test safely. 2. The cardiac stimulator cannot conduct pace-making and pace the heart or fail to measure the electrical conduction time. 3. The investigators fail to operate and collect data in accordance with the test requirements. In order to avoid test failure, the investigators shall be fully trained, the subjects shall be fully informed, and the study shall be conducted in strict accordance with the trial protocol.

## **12 Quality control of clinical trial**

### **12.1 Monitoring of clinical trial**

Study monitors are individuals who are appointed to be responsible for monitor the progress of study. The monitors are all properly trained and qualified to monitor the progress of clinical study. The study sponsor may appoint additional monitors at any time during the study. For additional information about the staff responsible for monitoring, please contact the sponsor.

The monitoring of the sponsor (or the representative) will visit each investigator prior to any procedure to ensure compliance with the following criteria:

The investigators understand and accept the obligation to conduct clinical study in accordance with the study protocol and applicable regulations, and hereby sign the clinical study agreement.

The investigators and their staff have sufficient time and facilities to conduct the study, and can access to a sufficient number of appropriate subjects for trial.

Original material shall be provided to prove the appropriateness of informed consent procedure, compliance with the study protocol, adequate reporting and follow-up of adverse events, accuracy of data collected in CRF and device information. The investigators/study site will be approved to access to such records. The study site shall maintain the signature log of monitoring visit. The investigators shall agree to take sufficient time to cooperate with the monitoring process and the investigators and/or study coordinator shall be present during the monitoring visit. The investigators shall provide the study supervisor with appropriate working environment for the purpose of reviewing study related documents.

